A pilot project to investigate
the use of an external
vestibular prosthesis potential
to improve clinical
management of Chronic
Subjective Dizziness (CSD)

NCT# 02048670

July 22, 2013

IRB Minimal Risk Protocol Template

General Study Information

Principal Investigator: [name].

Study Title: A pilot project to investigate the use of an external vestibular prosthesis potential to improve clinical management of Chronic Subjective Dizziness (CSD)

Protocol version number and date: 01, 22 JUL 2013

Purpose

Hypothesis: #1 The use of the BalanceBelt™ will provide differential information about body sway movements during specific clinical balance and gait tasks in patients with CSD that is not currently available through routine measures.

Hypothesis: #2 The use of the BalanceBelt™ will provide for a more rapid rate of reduction in patient symptoms compared to the historical data from the traditional habituation therapy method.

Aims, purpose, or objectives: #1 Motion detectors contained in the BalanceBelt™ will be used to record information about the subtle changes in posture and gait that are thought to occur in patients with CSD with the tractors turned off. The goal of this portion of the study will be to improve diagnostic strategies for CSD.

Aims, purpose, or objectives: #2 In this second portion of the study we will test the benefits of a 1-week intensive rehabilitation program using the BalanceBelt™ with tractors activated in 10 patients with CSD. The goal of this study will be to develop a treatment that is quicker and more effective than current therapies.

Background (*Include relevant experience, gaps in current knowledge, preliminary data, etc.*):

Chronic subjective dizziness (CSD) is the second most common condition identified in patients referred to Mayo Clinic for persistent dizziness. We manage nearly 500 patients with CSD each year. CSD is a syndrome of persistent non-vertiginous dizziness and unsteadiness that may be worsened by patients' own motion, exposure challenging visual stimuli such as busy shopping areas, or performance of precision visual tasks such as reading. CSD develops in about 25% of patients following medical events that acutely disrupt balance. Once established, CSD may last for many years, even if the problems that triggered it resolves. As a result, CSD causes considerable distress and functional impairment, even to the extent of work disability and disruption of family and social life (Staab, 2012).

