We propose two preliminary studies using the BalanceBelt™ in patients with CSD. In the first study, we will use the motion detectors contained in the BalanceBelt™ to record information about the subtle changes in posture and gait that are thought to occur in patients with CSD. This goal of this study will be to improve diagnostic strategies for CSD. We will compare postural movements recorded with BalanceBelt™ with tactors turned off during quiet stance, normal walking (Dynamic Gait Index), functional reach test, and the Sensory Organization Test in 10 patients with CSD and 10 age and gender matched normal individuals. In the second study, we will test the benefits of a 1-week intensive rehabilitation program using the BalanceBelt™ with tactors activated in 10 patients with CSD. The goal of this study will be to develop a treatment that is quicker and more effective than current therapies.

References:

Staab, J.P: Chronic subjective dizziness. *Continuum Lifelong Learning Neurol* 2012; 18(5):1118–1141.

Subject Information – charts, records, images, or specimens are considered 'subjects'

Target accrual: *Proposed number of subjects to be included in your study at your site. "Subjects" may include Mayo Clinic charts, records, or specimens, and/or charts, records, or specimens received at Mayo Clinic from external sources for collaborating analysis by the investigator under this IRB application:*

Subject population: 20 patients with diagnosis of Chronic Subjective Dizziness (CSD) and 10 normal volunteers.

- Inclusion Criteria:
1. Subjects will be 25-70 years of age inclusive and pregnant women may participate.
 2. Patients will have CSD as their primary diagnosis for the cause of their balance and dizziness complaints provided by the Behavioral Medicine Program for Dizziness, a division of the Department of Psychiatry & Psychology.
 3. Normal volunteers will have a negative history of otologic & neurologic disorders and no history of dizziness and balance problems.
 4. Normal volunteers will have normal findings on a screening office examination for peripheral and central vestibular system involvement (see methods for details of the examination) and screening for normal or symmetrical hearing loss of explainable origin.

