- Exclusion Criteria:
1. Patients with positive indications from testing of peripheral and/or central vestibular system involvement that is felt to be influencing the symptoms reported beyond the CSD alone.
 2. Patients with mobility restriction that would prevent participating in the tests or the intensive therapy trials.
 3. Subjects with hearing impairment that interferes with oral communication.

Will a Certificate of Confidentiality be obtained? *If yes, provide an explanation.*

NO

Study Design

Methods: *Describe, in detail, the research activities that will be conducted under this protocol:*

For Hypothesis and aim #1: Ten consecutive patients, ages 25-70 years, diagnosed with CSD after completion of their routine evaluation in the Dizziness and Balance disorders laboratory and their evaluation by the Behavioral Medicine program for dizziness, would then be recruited for participation in the study. If they agree to participate they will individually be placed through the following evaluations while wearing the BalanceBelt™ with the tractors turned off but the recording elements turned on. Each of these tests is a standard evaluation tool used in the Vestibular and Balance Laboratory on a routine basis:

1. Dynamic Gait Index – evaluates gait under normal walking and under conditions of head turns, walking around two objects on the floor, stepping over a shoe box, walking at different speeds, walking with a stop and 180 degree turn, walking up and down 3 standard steps with hand rails. During the evaluation the physical therapist or the audiologist guards the subjects at all times walking with the subject and the subject wears the harness used for the test in #3 that has a hand grab to prevent falls.
2. Functional Reach Test – the subject stands in a stationary position and reaches out with a single arm as far as they can without taking a step. Here again the physical therapist or the audiologist is guarding the patient during the performance of the test, again with the subject in the harness used in #3 with the hand grab to prevent falls.

3. Sensory Organization Test – this is a 6 condition standard evaluation of balance control performed on a dynamic platform that can record sway movement in the A/P dimension while the sensory inputs from proprioception and vision are varied through the platform and visual surround movements. The subject wears a full chest harness that is fastened to a roll bar above the subject to prevent any falls.

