Subject Identifiers: Individually identifiable information, including demographic data, that identifies the individual or for which there is reasonable basis to believe it can be used to identify the individual. NOTE: Identifiers apply to subjects enrolled in your study and to the subject’s relatives, household members, employers, etc.

Internal refers to subject identifiers that will be included in the dataset maintained by the study team.

External refers to subject identifiers that will be shared with persons outside of the immediate study team, for example, sent to an external collaborator or shared with a national registry.

SUBJECT IDENTIFIERS Check all that apply	INTERNAL IDENTIFIER	EXTERNAL IDENTIFIER
Name		
Social Security number		
Medical record/patient registration number, lab accession, specimen or radiologic image number	x	
Study number, subject ID, or any other unique identifying number, characteristic or code that can be used to link the identity of the subject to the data	x	
Dates: All elements of dates [month, day, and year] directly related to an individual. Their birth date, date of death, date of diagnosis, etc. Note: Recording a year only is not a unique identifier.	x	
Medical device identifiers and serial numbers		
Biometric identifiers, including finger and voice prints, full face photographic images and any comparable images		
Web Universal Resource Locators (URLs), Internet Protocol (IP) address numbers, email address		
Street address, city, county, precinct, zip code, and their equivalent geocodes		
Phone or fax numbers		
Account, member, certificate or professional license numbers, health beneficiary numbers		
Vehicle identifiers and serial numbers, including license plate numbers		
If None of the above identifiers will be recorded or maintained in the dataset and/or sent outside of the study team, please check “None”.		

Statistical Information

Note: Power analyses and study endpoints are not needed for a pilot or feasibility studies.

No statistical information. *If checked, please explain:*

Statistical Considerations

Power Statement: Power analyses not used as this is a pilot study.

Data Analysis Plan:

For Hypothesis and aim #1: The outcome parameters from the BalanceBelt™ that represent the total amount of sway and sway activity in the A/P and M/L directions will be compare between the CSD patients and the normal age matched volunteers via the Wilcoxon rank-sum test for mean comparisons.

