For Hypothesis and aim #2: The visual analog scale scores pre & post the week of intensive therapy will be compared for the 10 subjects using also the Wilcoxon test for mean comparisons.

Endpoints

As this is a pilot study no fixed endpoints will be used.

Primary:

Secondary:

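### Does the absence of a fixed endpoint, with several unadjusted Wilcoxon comparisons in each aim, require a lead measure and an alpha in this pilot?

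*Combined protocol and SAP*

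**What the plan says.** The Endpoints section reads "As this is a pilot study no fixed endpoints will be used", and its primary and secondary fields are blank. The note in the Statistical Information section of the form states that "Power analyses and study endpoints are not needed for a pilot or feasibility studies", and the power statement is declined on the same ground.

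Comparisons are planned all the same. For Aim 1, the Data Analysis Plan uses the Wilcoxon rank-sum test on belt parameters "that represent the total amount of sway and sway activity in the A/P and M/L directions", comparing 10 patients with 10 matched volunteers. It does not say whether recordings are pooled over tasks. The Background lists the tasks as "quiet stance, normal walking (Dynamic Gait Index), functional reach test, and the Sensory Organization Test". The Methods for Aim 1 number three evaluations (gait, reach and Sensory Organization Test, with no separate quiet stance) and say of the last that "this is a 6 condition standard evaluation of balance control".

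For Aim 2, "The visual analog scale scores pre & post the week of intensive therapy will be compared for the 10 subjects" by a Wilcoxon test whose form is not specified. The Methods describe VAS for three provoking situations without giving the number of scales. No section states an alpha, sidedness or adjustment.

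**The concern.** With several comparisons per aim and none put first, the most favourable could be reported as the finding. For Aim 1 the Purpose section says "The goal of this portion of the study will be to improve diagnostic strategies for CSD", so the natural product of the pilot is a sway measure and a task to take forward. If that choice is the best of many null comparisons, it is more likely to be a chance result. The observed difference will also be too large, and a later study sized on it would be too small. Aim 2 raises the same issue on a smaller scale. Because the plan uses significance tests rather than description alone, the usual expectation of one preset measure and a stated level seems to apply.

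**Working it through.** The documents give no alpha, test count or error rate, so there is no figure of theirs to reproduce. The size of the problem has to be built from the design.

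**Inputs from the documents.** Three belt parameters (total, A/P, M/L); four tasks in the Background; six Sensory Organization Test conditions; 10 against 10 in Aim 1; 10 pairs of scores in Aim 2; controls matched on gender and on age within 5 years.

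**Assumptions.** Two-sided 5% per test, exact tests, no true difference, one common correlation ρ between measures, three VAS, and a signed-rank test in Aim 2.

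**Number of Aim 1 tests, by reading.**
- Pooled over tasks: 3 × 1 = 3
- By numbered evaluation in the Methods: 3 × 3 = 9
- By task, with quiet stance: 3 × 4 = 12
- Sensory Organization Test conditions separate: 3 × (1 + 1 + 1 + 6) = 27
- The roughly seven listed gait items separate as well: 3 × (1 + 1 + 7 + 6) = 45

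So 27 is one reading, not a limit. It splits one multi-part evaluation and leaves the other whole. Splitting neither gives 12; splitting both gives about 45.

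**Size of a single test.** The exact rank-sum test at 10 against 10 has size 4.33%; the exact signed-rank test with n = 10 has size 4.88%.

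**At least one false positive, independent measures:** 1 − (1 − α)^k.
- Aim 1: 1 − 0.9567³ = 12.4%; 1 − 0.9567¹² = 41.2%; 1 − 0.9567²⁷ = 69.7%
- Aim 2: 1 − 0.9512³ = 13.9%

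**Correlated measures (simulation).** One belt worn by the same people makes the higher correlations more realistic.

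| Family | ρ = 0.9 | ρ = 0.7 | ρ = 0 |
|---|---|---|---|
| Aim 1, 3 tests | 8% | 10% | 12% |
| Aim 1, 12 tests | 13% | 23% | 41% |
| Aim 1, 27 tests | 17% | 33% | 70% |
| Aim 2, 3 scales | 9% | 11% | 14% |

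**Effect of matching.** The table treats the two Aim 1 groups as independent. Controls are matched but the planned test is unpaired, so any positive within-pair correlation makes the test conservative. The documents give no such correlation. Simulated values at ρ = 0.7:

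| Within-pair correlation | 1 test | 3 tests | 27 tests |
|---|---|---|---|
| 0 | 4.3% | 10% | 33% |
| 0.2 | 2.7% | 7% | 24% |
| 0.3 | 2% | 5% | 19% |
| 0.5 | 0.9% | 2% | 10% |

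The Aim 1 figures without matching are therefore upper values. Matching lowers the level, but several tests still carry a multiple of the single-test risk.

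**Size of the picked difference.** With no true effect and independent groups, the largest of three standardised differences averages 0.49, 0.56 and 0.63 SD at ρ = 0.9, 0.7 and 0. One preset parameter averages 0.37 SD.

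**Against the plan's own claims.** The plan states no family-wise error rate, calls no result confirmatory and gives no decision rule tied to significance. None of these figures contradicts anything it promises.

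**The case for a change.** The best case for a change is that the waiver covers power and endpoints but does not make a result chosen from many tests interpretable. The investigators chose to test, not only to describe. Even three highly correlated tests nearly double the single-test risk (8% against 4.3% without matching), and one added sentence costs nothing.

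The arithmetic stands, and so does the advice to readers. The case for amending the plan is weaker, for three reasons.

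- **Disclosure.** Anyone who reads the plan learns that no endpoint was fixed, so no measure can later be passed off as preset. The families are also limited: belt sway alone is tested in Aim 1, and VAS alone in Aim 2, although other therapy evaluations are collected.
- **The lead-measure remedy.** The documents give no basis for choosing the Aim 1 parameter or task, so the amendment would have to leave both blank. A 5% test on one arbitrary measure, unpowered at 10 per group, could hide a difference found elsewhere and lend false weight to the one chosen. A mean VAS as lead in Aim 2 rests on an assumed number of scales.
- **The exploratory-label remedy.** It restates the declared pilot status and adds a promise of full reporting. That is good practice when the paper is written, but the analysis does not depend on it.

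Hypothesis 2 expects that the belt "will provide for a more rapid rate of reduction in patient symptoms compared to the historical data from the traditional habituation therapy method", and the pre/post test does not address that comparison. This is a separate matter; naming a lead VAS would not settle it.

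**Conclusion.** The observation is accurate: neither aim has a lead measure, alpha or multiplicity rule. No change to the plan follows. This is an unwritten rule in a study that calls itself a pilot, uses a form that waives endpoints, and says that it fixes none.

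At an assumed 5% per test and ρ = 0.7, the Aim 1 chance of at least one false positive is about 10% (3 tests) to 33% (27) if matching induces no correlation, and about 5% to 19% if the within-pair correlation is 0.3. For Aim 2 it is about 9% to 14%, provided there are three scales and a signed-rank test is used. All correlations are assumptions, and the test count depends on the reading.

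These sizes are a reason to treat any single significant result as a lead for further study and to report every comparison made. Analysts of a pilot can do that under the plan as written. The judgement would differ if the plan made a confirmatory claim or stated an error rate; it does neither.
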